### CONFIDENTIAL

This document is a confidential communication of Consumer Product Testing Company, Inc. containing Testing Facility capabilities and processes, and as such, is intended solely for the use of the Sponsor and Testing Facility in the performance of services. The confidential information contained herein, shall only be released by either Party upon compelled disclosure in compliance with legal or regulatory requirement.

5. Requests an early discontinuation due to:
  - A clinical event for which the PI did not consider removal from the trial to be necessary;
  - Other (non-specific) subject-initiated reason.

## 5.6 Disposition of Withdrawn Subjects

The date the subject is withdrawn from the trial and the reason for discontinuation will be recorded on the Case Report Form (CRF). Attempts will be made to conduct all evaluations scheduled for the final trial visit as soon as possible after the subject is withdrawn from the trial.

When a subject fails to return for scheduled trial visits, the PI will make a reasonable effort to contact the subject and determine why the subject failed to return. This information will be recorded on the CRF. When a subject is withdrawn from the trial (regardless of the reason), the PI will encourage the subject to complete all evaluations which may be necessary to assure that the subject is free of untoward effects, and to seek appropriate follow-up for any continuing problem.

## 6 Methodology

Each potential subject must provide informed consent before participating in the trial. The informed consent process fully apprises the potential subject of the risks and benefits to them and to society for participating in the trial. The Informed Consent Form (ICF) will clearly state that designated Testing Facility personnel will be able to view each potential subject's medical records. If the potential subject agrees to participate in the trial, the potential subject will execute the ICF with their signature and date. The CPT staff who conducted the informed consent process will also execute the document by signing and dating the ICF. Each subject will be given a signed copy of the Informed Consent Form. If the subject has questions about their rights, they may contact a Subject Rights Advocate at any time during or after trial participation. The length of the trial is expected to be 3-10 days.

Each task outlined in this methodology will be carried out by CPT staff members that have been trained, per CPTs SOPs and policies, to perform those tasks.

CPT staff member(s) will complete the following screening procedures with subjects to confirm eligibility after informed consent is obtained:

- Check previously determined colorimetric ITA° value to ascertain if collection of a new value is needed. Sponsor requires an ITA° value >28°, determined by the Testing Facility by colorimetric methods (reference 12.1), be obtained within 1 week of trial participation.
- Inquire about any changes to medical and medication history on file via an MHF;
- Conduct a contraception check;
- Skin examination;
- Confirm that the subject meets the inclusion/exclusion criteria;

### CONFIDENTIAL

This document is a confidential communication of Consumer Product Testing Company, Inc. containing Testing Facility capabilities and processes, and as such, is intended solely for the use of the Sponsor and Testing Facility in the performance of services. The confidential information contained herein, shall only be released by either Party upon compelled disclosure in compliance with legal or regulatory requirement.

- For female subjects of childbearing potential, a urine pregnancy test will be administered, per the manufacturer’s instructions (subject urinates into paper cup, then inserts dipstick into urine per instructions, urine is dumped into toilet by subject) and test will be collected by laboratory staff. CPT staff will verify subject has disposed of urine. No urine is collected. Pregnancy test results will be noted on the Urine Pregnancy Test Results Log and the test dip stick will be disposed of in a waste receptacle. The urine pregnancy test will have a sensitivity of at least 25 mIU/mL. A negative pregnancy result is required before any test material is applied to the subject. Pregnancy tests may be repeated when potential pregnancy is suspected during participation in the trial (e.g., one menstrual cycle is missed during the testing period), as per request of the IRB, or if required by local regulations. In the case of a positive confirmed pregnancy, the subject will be withdrawn from the trial.

**6.1 Instrumentation**

Xenon arc solar simulators (150 W or 300 W) equipped with WG320 and UG11 filters shall be used as the source of full spectrum UV radiation (Solar Light Company, Philadelphia, PA). This instrument, described in detail (reference 12.4), provides a stable, continuous spectral output in both the UVB range (290 nm – 320 nm) and the UVA range (320 nm – 400 nm) that is similar to sunlight. Qualified technician(s) trained in the use of this instrument will be responsible for its operation.

The performance of the solar simulators depends on the spectral output. Therefore, the solar simulator spectral output specification is described in terms of cumulative erythema effectiveness by successive wavelength bands from 290 nm to 400 nm. The erythema effectiveness of each wavelength band is expressed as a percentage of the total erythema effectiveness from less than 290 nm to 400 nm, or as the Relative Cumulative Erythema Effectiveness (% RCEE). The maximal irradiance is confirmed to avoid the feeling of excessive heat during the irradiations. The following table indicates the % RCEE acceptable output limits for the solar simulators.

Spectral Range (nm)	Measured % RCEE	
	Lower Limit	Upper Limit
<290		<0.1
290-300	1.0	8.0
290-310	49.0	65.0
290-320	85.0	90.0
290-330	91.5	95.5
290-340	94.0	97.0
290-400	99.9	100.0

Additionally, the total radiometric proportion of the solar simulator UVAI irradiance and UVAIL irradiance shall be ≥60% and ≥20%, respectively, of the total UV irradiance.

Solar simulators shall be provided an appropriate warm-up period, after which, they are expected to have no significant time-related fluctuations in radiation emissions. Each solar simulator shall have good beam uniformity in the exposure plane and shall meet the % RCEE

**CONFIDENTIAL**

This document is a confidential communication of Consumer Product Testing Company, Inc. containing Testing Facility capabilities and processes, and as such, is intended solely for the use of the Sponsor and Testing Facility in the performance of services. The confidential information contained herein, shall only be released by either Party upon compelled disclosure in compliance with legal or regulatory requirement.

acceptance limits for UV solar simulator output. Total irradiance shall not exceed 1,600 W/m^2. The minimal beam irradiance at any subsite shall not be lower than 10% below the maximum beam irradiance at any subsite.

The lamp output shall be measured after warm-up with a UV intensity meter (Model PMA2100, Solar Light Company, Philadelphia, PA) equipped with the appropriate detector before and after the test period. To ensure that solar simulators deliver the appropriate spectrum of UV radiation, their spectral output shall be measured semi-annually with an accurately calibrated spectroradiometer.

All instruments shall be calibrated and maintained per CPT's SOPs.

## 6.2 Determination of Minimal Erythral Dose (MEDu)

### 6.2.1 Methodology

Within 1 week prior to the test material phase, a provisional MEDu of each subject shall be determined by a progressive sequence of timed UV radiation exposures, each of which shall be graduated incrementally by 25% over that of the previous exposure. The test sites shall be evaluated for erythema according to the MED Scoring Scale (Section 6.2.2). The MED is the lowest dose of UVR that produces the first perceptible unambiguous erythema with defined borders appearing over most of the field of UV exposure, 16 h to 24 h after UV exposure (Score of 1 or greater on the MED Scoring Scale).

On the same day as the test material is irradiated, an MEDu shall be determined by a progressive sequence of timed UV radiation exposures. The exposures shall be graduated incrementally by 25% over that of the previous exposure, and the graduation must be consistent with that of the MEDp test sites. Further, the MEDu test site must be in close proximity to the MEDp test sites. The Test sites shall be evaluated for erythema according to the MED Scoring Scale (Section 6.2.2). The MED is the lowest dose of UVR that produces the first perceptible unambiguous erythema with defined borders appearing over most of the field of UV exposure, 16 h to 24 h after UV exposure (Score of 1 or greater on the MED Scoring Scale).

### 6.2.2 MED Scoring Scale

Score	Description
0	No reaction
0.5	Equivocal reaction, barely perceptible erythema with no clearly defined border
1	Mild but definite erythema with clearly defined borders
2	Moderate clearly defined erythema
3	Strong erythema, edema
4	Bulla or vesiculation

## 6.3 Determination of Minimal Erythmal Dose on Protected Skin (MEDp)

### 6.3.1 Test Material Application

The test sites expected to be used in this trial will be 40 cm^2. A sufficient number of 40 cm^2 test sites shall be outlined with a surgical marking pen on the subject's back between the scapulae and the beltline, lateral to the midline, while avoiding any anatomical areas containing extreme curvature. The lines shall be drawn on the subject while in the testing position (upright or prone). These test sites shall be designated for the test material(s) and control standard, with an adjacent test site designated for a concurrent MEDu determination (Section 6.2.1).

Assignment of the test sites for test material(s), control standard, and MEDu shall follow a randomization schedule generated using a validated version of the statistical software R 3.6.1. For each subject, 4 test sites will have a random assignment number for up to two test materials, control standard, and MEDu, with at least 3 of the test sites being utilized for application. If a subject is tested at only 3 test sites, the subsequent randomization assignment will also involve only 3 test sites, with the corresponding test material used as the primary assignment to maintain balancing of treatment allocation.

Test material preparation, test material application, UV exposures, and MED assessments shall each be performed by trained technicians in ambient conditions (18-26°C) according to CPT's SOPs and the International Standard Test Method (reference 12.1).

A portion of test material(s) or control standard shall be applied to the appropriate 40 cm^2 test site and spread evenly over the test site using a finger cot that has not been pre-saturated with the test material or control standard. This application shall provide a test material film of approximately 2.00 ± 0.05 mg/cm^2, using 80 ± 2 mg of material. The actual weight applied shall be recorded on the CRF. To aid spreading, droplets of test material or control shall be deposited within the test site, and then spread over the whole test site using light pressure. Spreading time should be in the range of 35 ± 15 seconds.

There must be a minimum distance of 1 cm between the borders of adjacent test material application test sites, and the test sites must be randomly distributed on the subject's back and throughout the panel. The area of each subsite shall be at least 0.5 cm^2 and the distance between borders of each subsite shall be at least 0.8 cm. The minimum distance between any subsite and the edge of its test site shall be 1 cm.

### 6.3.2 UV Exposures

Between 15 and 30 minutes after test material or control standard application, all test sites shall be divided into 6 subsites which shall receive a progressive sequence of timed UV radiation exposures. UV exposures shall be selected for each subsite based upon the previously determined MEDu, as described in

#### CONFIDENTIAL

This document is a confidential communication of Consumer Product Testing Company, Inc. containing Testing Facility capabilities and processes, and as such, is intended solely for the use of the Sponsor and Testing Facility in the performance of services. The confidential information contained herein, shall only be released by either Party upon compelled disclosure in compliance with legal or regulatory requirement.

Section 6.2.1, and the expected SPF of the test material(s) or of the control standard.

The exposure shall be increased in geometric progression, using the following dose increments in relation to the expected SPF values:

Test Site	Expected SPF	Dose Increment
MEDu	N/A	1.25 (25%)
P2 Standard	16.1	1.25 (25%)
Test Material(s)	15	1.25 (25%)

Subjects will be in the same position (either prone or seated upright) used during test material application, irradiation, and MED assessments. After irradiation is completed, the control standard and test material(s) may be gently removed using a cotton pad with a mild lotion such as makeup remover or other similar product.

### 6.3.3 Evaluation

After irradiation is completed, all immediate responses will be recorded on a CRF. These include several types of typical responses such as immediate reddening, immediate darkening or tanning, and an immediate generalized heat response. After immediate responses are noted, each subject will be required to shield the exposed test areas from further UV radiation until evaluation of the test sites the following day.

The MEDu, MEDp, and the MED for the control standard will be evaluated by a trained CPT staff member 16 to 24 hours after UV exposure to determine an MED. The MED is the lowest dose of ultraviolet radiation (UVR) that produces the first perceptible unambiguous erythema with defined borders appearing over most of the field of UV exposure, 16 h to 24 h after UV exposure (a score of 1 or greater on the MED Scoring Scale). Evaluations will be conducted in a room with matte, neutral wall colors and under uniform illumination of at least 450 lux with the subject in the same position (either seated upright or prone) as when the subject was irradiated.

In order to maintain the blinding and to avoid introducing any bias, the person who evaluates the MED responses shall not be the same person who applies the test material or control standard or administers the UV radiation (i.e., blinded evaluator).

## 7 Statistical Methods

### 7.1 Rejection of Data

Test data from a qualified subject shall be invalid and rejected for any of the following reasons:

- If the exposure series fails to elicit an MED response on either the treated or unprotected test sites;
- If the responses on the treated test sites are randomly absent (which indicated the test material (or control standard) was not spread evenly);
- If all subsites on the exposure series show an erythema response upon evaluation; or
- If the subject was noncompliant (e.g., subject withdraws from the test due to illness or work conflicts; subject does not shield the exposed test sites from further UV radiation until the MED is read, etc.).

If data are rejected for any one test material on more than 5 qualified subjects, then the entire test for that material is invalid and shall be rejected. If data are rejected for the control standard (Reference Sunscreen Formulation) on more than 5 qualified subjects, then the entire test is invalid and shall be rejected.

### 7.2 SPF Calculation for a Test Material on a Subject

The SPF is defined as the ratio of the energy of exposure to full spectrum UVR, 290 nm – 400 nm, to produce erythema in human skin in the presence of a test material (or control standard), applied at 2 mg/cm^2, to that in its absence and is calculated as follows:

$$\text{SPFi} = \frac{\text{MED (protected skin)}}{\text{MED (unprotected skin)}} = \frac{\text{MEDp}}{\text{MEDu}}$$

SPFi is expressed to one decimal place.

### 7.3 SPF Calculation for a Test Material for the Panel

The SPF of the test material (or control standard) is defined as the arithmetical mean of all of the valid individual (SPFi) values obtained from the total number (n) of subjects used, expressed to one decimal point:

$$\text{SPF} = (\sum \text{SPFi}) / n$$

Its standard deviation(s) is:

$$s = \sqrt{[(\sum \text{SPFi}^2) - ((\sum \text{SPFi})^2 / n)] / (n-1)}$$

The 95% Confidence Interval (95% CI) for the mean SPF is expressed as:

$$95\% \text{ CI} = \text{SPF} - c \text{ to } \text{SPF} + c$$

#### CONFIDENTIAL

This document is a confidential communication of Consumer Product Testing Company, Inc. containing Testing Facility capabilities and processes, and as such, is intended solely for the use of the Sponsor and Testing Facility in the performance of services. The confidential information contained herein, shall only be released by either Party upon compelled disclosure in compliance with legal or regulatory requirement.

where c is calculated as:

$$c = (t \text{ value}) \times \text{SEM} = (t \text{ value}) \times s / \sqrt{n}$$

$$c = t \times s / \sqrt{n}$$

$$\text{CI}[\%] = 100 \times c / \text{SPF}$$

SEM = standard error of the mean

n = total number of subjects used

t = t value from the "two-sided" Student-t distribution table at a probability level  $p = 0.05$  and with degrees of freedom  $\nu = (n-1)$

The statistical criterion for all SPF measurements is that the 95% CI on the mean SPF measured shall fall within a range of  $\pm 17.0\%$  of the measured mean SPF. This applies to test material SPF measurement and control standard SPF measurement.

Consequently, the actual number of subjects tested is defined as the number (minimum ten) required to produce a mean test material (or control standard) SPF with a 95% CI, which

falls within a range of  $\pm 17.0\%$  of the measured mean SPF for the test material and a mean reference SPF which has a 95% CI that falls within the range of  $\pm 17.0\%$  of the measured mean SPF for the control standard.

A minimum of 10 valid results is only sufficient if the statistical criterion is fulfilled. If not, the number of subjects may be increased from ten until the statistical criterion is met up to a maximum of 20 valid results (i.e., a maximum of 20 valid results plus 5 rejected invalid results). **Note that for this trial the Sponsor has set a maximum of 15 subjects. Written approval is needed from Sponsor if more than 15 subjects are required.** For details on the sequential procedure and calculations, see reference 12.1.

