**CONFIDENTIAL**

This document is a confidential communication of Consumer Product Testing Company, Inc. containing Testing Facility capabilities and processes, and as such, is intended solely for the use of the Sponsor and Testing Facility in the performance of services. The confidential information contained herein, shall only be released by either Party upon compelled disclosure in compliance with legal or regulatory requirement.

**Randomization:** A method of assigning trial test material such that each subject has an equal chance of being assigned to each treatment or control group. Randomization guards against selection bias.

**Serious Adverse Event (SAE):** Any adverse event (AE) that is fatal, life-threatening, or permanently disabling, or that results in new or prolonged hospitalization, in a congenital anomaly/birth defect, or is an important medical event.

**Source Data:** All information contained in original records and certified copies of results or observations.

**Source Document:** A document or form that is used to capture original, trial-related data or information. A source document may serve as the Case Report Form or the information may be transcribed onto a Case Report Form.

**Sponsor:** Individual, company, institution, or organization that takes responsibility for initiation, management, and financing of research.

**Standard Operating Procedures (SOPs):** Official, detailed, written instructions for the management of clinical trials. SOPs ensure that all the functions and activities of a clinical trial are carried out consistently and efficiently.

**Subject:** A patient or healthy person participating in a research trial.

**Sun Protection Factor (SPF):** The arithmetic mean of all valid individual SPFi values obtained from all subjects in the test.

**Test Area:** The area of the back between the scapula line and the waist.

**Test Material:** Any material or product that is the subject of testing or a clinical trial. This may also be referred to as a "test article" or "investigational material".

**Test Site:** The site where a test material or control standard is applied or the site used for the determination of the unprotected MED.

**Test Subsite:** An area within the test site that is exposed to UVR.

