## 4 Test Materials

### 4.1 Identification

ChapStick Moisturizer, Classic Flavor (CCI) and ChapStick Moisturizer, Strawberry Flavor (CCI) will be uniquely identified by a CPT trial number. CPT will record the test material name, physical description, lot number (if available), Sponsor, and date received into the log-in database. Each of the two test materials has an expected SPF of 15.

A control standard (Reference Sunscreen Formulation) will be run concurrently with the test materials. Three control standards are delineated within the methodology as follows:

Control Standard	Mean SPF	Acceptance Limits (Mean $\pm$ 2SE)	
		Lower limit	Upper Limit
P2	16.1	13.7	18.5
P3	15.7	13.7	17.7
P7	4.4	4.0	4.8

For the two test materials in this trial, control standard P2 will be used.

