### CONFIDENTIAL

This document is a confidential communication of Consumer Product Testing Company, Inc. containing Testing Facility capabilities and processes, and as such, is intended solely for the use of the Sponsor and Testing Facility in the performance of services. The confidential information contained herein, shall only be released by either Party upon compelled disclosure in compliance with legal or regulatory requirement.

valid results from a maximum of 25 subjects, then the test shall be rejected. For details on the sequential procedure and calculations, see reference 12.1.

Subjects who meet all of the inclusion criteria (Section 5.2) and none of the exclusion criteria (Section 5.3) will qualify for trial participation. Subjects cannot all be of the same skin phototype.

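### Does the plan leave open what happens if the P2 control mean falls outside its acceptance limits?

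*Combined protocol and SAP*

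**What the plan says.** Section 4.1 tabulates three reference formulations, introduced as set out in the test methodology. Each has a mean and lower and upper acceptance limits described as mean ± 2SE. For P2 these are 16.1, 13.7 and 18.5. The section then states: "For the two test materials in this trial, control standard P2 will be used".

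The rules that act explicitly on the control come later:

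- Section 7.3: "The statistical criterion for all SPF measurements is that the 95% CI on the mean SPF measured shall fall within a range of" plus or minus 17.0% around that mean. This covers the test materials and the control.
- Section 5.1: if that criterion is still unmet after 20 "valid results from a maximum of 25 subjects, then the test shall be rejected".
- Section 7.1, for a material: "If data are rejected for any one test material on more than 5 qualified subjects, then the entire test for that material is invalid".
- Section 7.1, for the control: "If data are rejected for the control standard (Reference Sunscreen Formulation) on more than 5 qualified subjects, then the entire test is invalid".

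On which results form the P2 mean, the Definitions take SPF as the mean of the valid individual "values obtained from all subjects in the test". Section 7.3 gives the same definition for a test material or the control. Section 6.3.1 allows a subject to carry only one of the two materials: "If a subject is tested at only 3 test sites, the subsequent randomization assignment will also involve only 3 test sites".

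Section 7.4 promises a pass or fail grade in the listing. Section 11.8 puts the control's individual MEDs, its SPFi values and the mean SPFs with their intervals in the final report.

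**The concern.** SPF is the only endpoint, and P2 is the one check on the whole procedure that is expressed in SPF units with numeric limits. Lamp output and applied weight are also checked, but neither shows whether a product of known SPF reads correctly.

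Read literally, Sections 5.1, 7.1, 7.3 and 7.4 reject a control for too many invalid results or too wide an interval, never for a mean in the wrong place. The interval rule cannot stand in for the limits, because it is relative to whatever mean was measured. Section 7.4 names no criterion for its grade. Because some subjects may receive one material only, P2 could also be averaged over the whole test or separately over the subjects supporting each material.

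If these points were truly open, the consequence of a poor control, and whether it touched one material or both, could be settled after the product SPFs were known.

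**Working it through.** **Inputs.** P2 mean 16.1 and limits 13.7 to 18.5 (Section 4.1). CI[%] = 100 × t × s / (√n × SPF), two-sided 5%, n − 1 degrees of freedom, bound 17.0% (Section 7.3). At least 10 valid results, and 15 subjects unless the sponsor approves more (Sections 5.1 and 7.3). Dose step 1.25 (Section 6.3.2: "The exposure shall be increased in geometric progression, using the following dose increments in relation to the expected SPF values"). The plan gives no between-subject CV, so 10%, 15% and 20% are assumptions.

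**The limits agree with themselves.** Midpoint (13.7 + 18.5)/2 = 16.1. Half-width 2.4, so the implied SE is 2.4/2 = 1.2.

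**The CI rule does not test location.** Since s/SPF is the CV, CI[%] = 100 × t × CV/√n, and the mean drops out. The largest CV that passes is 17.0 × √n / t:

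| n | t | CV ceiling |
|---|---|---|
| 10 | 2.262 | 23.8% |
| 15 | 2.145 | 30.7% |
| 20 | 2.093 | 36.3% |

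**Panels that pass the CI rule outside the limits.** Assume one subsite sits at the expected SPF. One step up is 16.1 × 1.25 = 20.1 and one step down is 16.1/1.25 = 12.9.

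- Seven results at 20.1 and three at 16.1: mean 18.9, s = 1.93, c = 2.262 × 1.93/√10 = 1.38, CI[%] = 7.3.
- Eight at 12.9 and two at 16.1: mean 13.5, s = 1.35, c = 0.97, CI[%] = 7.1.

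**How often.** Simulated panels of 10 to 15 results, read on 1.25 steps and stopped once the CI rule is met, give this share of CI-passing panels with a P2 mean outside the limits:

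| True P2 mean | CV 10% | CV 15% | CV 20% |
|---|---|---|---|
| 16.1 (stated) | 0.05% | 0.8% | 2.5% |
| 17.0 (assumed) | 2% | 6% | 10% |

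If the control were badly off, the limits would do the work. With 10 normally distributed results and a true mean of 13.0 or 20, between 63% and 94% of panels pass the CI rule and lie outside the limits (CV 15% to 20%).

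**Whole-test or per-material P2.** Take 15 subjects and 10 per material. The overlap is then 10 + 10 − 15 = 5, the smallest possible. Use true mean 16.1 and CV 20%, so s = 3.22.

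- One whole-test mean, n = 15: SE = 3.22/√15 = 0.831, z = 2.4/0.831 = 2.89, chance outside 0.4%.
- One per-material mean, n = 10: SE = 3.22/√10 = 1.018, z = 2.36, chance outside 1.8%.
- At least one of the two per-material means outside, by simulation: about 3%.

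P2 is on target throughout this scenario, so the extra failures are all false.

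**The case for a change.** The strongest case for a change is that Section 7.4 says all statistical methods are in the protocol and uses that to dispense with a separate analysis plan. Sections 5.1 and 7.3 send the reader to ISO 24444 only for the sequential procedure and calculations. The protocol writes out its other rejection rules, so this one is conspicuously absent, and one sentence would supply it. The Definitions also describe a panel by its combination of materials, and Section 5.1 records results by panel, which could suggest separate P2 means.

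Part of this stands. The consequence is not restated, the CI rule cannot replace it, and the grade's criterion is left to inference. ISO 24444 itself was not available, so nothing here relies on its content.

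The rest does not carry. Sections 1 and 2 adopt the ISO method for the trial, and Section 4.1 presents the limits as part of that method. Saying that an out-of-limits panel meets every written rule treats limits labelled as acceptance limits as if they were not one. On the P2 set, the SPF definition, the Section 7.3 formula and the whole-test consequence of control rejections in Section 7.1 all favour a single mean over all valid subjects. A per-material rule would depart from that default.

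**Conclusion.** The omission is real, but it is missing detail that an analyst following the plan fills sensibly: compare the mean of all valid P2 results with 13.7 to 18.5, and do not accept the test if it lies outside. The pass or fail grade then rests on that check together with the existing rules in Sections 7.1 and 7.3. The values needed are already in the final report, so an out-of-limits control cannot pass unseen.

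The situation should be uncommon in a sound test: about 0.05% to 2.5% of CI-passing panels at the stated mean of 16.1, rising to about 2% to 10% if P2 truly averaged 17.0. These figures rest on assumed CVs of 10% to 20% and simulated reading on 1.25 steps.

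The only suggestion that would alter the analysis, a separate P2 set for each material, brings no clear gain. With P2 on target and CV 20%, it raises the chance of a control failure from 0.4% to about 3% in the 15-subject scenario with least overlap. No change to the plan follows.
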